5.7. Measurements

5.7.1. Outcome variables

Reducing heavy alcohol consumption: The main goal of the Aim 1 intervention is to reduce the level of drinking to a level most likely to decrease the risk of INH toxicity. Thus we have chosen no/non-heavy alcohol consumption as the Aim 1 primary outcome. While we are incentivizing negative urine EtG tests at INH refill visits as our *intervention*, our *trial outcome variable* captures reducing drinking over the six-month duration. We will consider PEth <35 ng/mL and AUDIT-C negative (modified to refer to the prior 3 months) at 3 and 6 months as refraining from heavy drinking during the entire period of risk. The AUDIT-C will be used because it is comprised of ranges for typical numbers of drinks and frequency of heavy drinking, rather than precise number of drinks consumed (as in the Timeline Follow Back), which can be difficult to quantify for the traditional and home-brewed beverages frequently consumed in rural African settings.^{99,157} We have adapted the AUDIT-C to cover the prior 3 months (as opposed to the past year) as a measure of current drinking, and use standard cutoffs (≥ 3 for women and ≥ 4 for men) to represent heavy drinking. We will use 35 ng/mL as the PEth cutoff as described above (see Preliminary Studies). We will examine other measures of heavy drinking in sensitivity analyses, including number of drinking days in the prior 30, number of heavy drinking days (defined as ≥ 4 or ≥ 5 drinks/occasion by women and men), and PEth as a continuous variable.

IPT adherence. As above, we are incentivizing positive IsoScreen tests at INH refill visits, but our second trial *outcome variable* is IPT adherence over the entire six months. While there is no gold standard for determining medication adherence, MEMS adherence has been highly predictive of undetectable HIV viral load,^{83,158,159} is considered the reference standard,^{72,83,160,161} and therefore will be our primary measure of adherence. MEMS adherence will be defined as the number of pill bottle openings (no more than 1 per day counted) divided by the number of prescribed doses (180, unless taken off the medication early). The primary outcome for Aim 2 will be the proportion of participants that achieve >90% MEMS adherence to INH during prescribed IPT. We will examine other measures of INH adherence in secondary analyses, including drug concentration (ng/mg) in hair samples at 3 and 6 months, and continuous MEMS adherence.

Hepatotoxicity. A secondary outcome will be treatment discontinuation due to a Grade 3/4 hepatotoxicity at any time during the treatment period. Grade 3/4 hepatotoxicity is defined as in previous trials³ as ALT or ALT $>3-5$ ULN and symptoms (nausea, vomiting, jaundice, or fatigue) or ALT or AST >5 ULN, regardless of symptoms. Study clinicians, blinded to intervention arm, will determine treatment discontinuation.

HIV viral suppression. The primary outcome for Aim 3 will be HIV viral suppression 12 months post-enrollment. We will also examine viral load six months post-enrollment as a secondary outcome for Aim 3.

Active TB. A secondary outcome for Aim 3 will be active TB at any time during the 12 months post-enrollment. Active TB will be defined as confirmed (if Xpert MTB/RIF assay positive) or suspected (based on chest x-ray findings or response to anti-TB treatment in symptomatic, Xpert assay negative persons).

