5.3. Enrollment and randomization

After eligibility is determined, we will enroll and randomize participants, using a 2x2 factorial design, to either, both, or neither of the incentive interventions, as follows:

Arm 1: No intervention control;

Arm 2: Escalating incentives for EtG negative urine tests;

Arm 3: Escalating incentives for IsoScreen positive urine tests;

Arm 4: Escalating incentives for EtG negative urine tests and for positive IsoScreens (rewarded separately) (Figure 1).
All participants will receive brief alcohol and adherence counseling according to Uganda Ministry of Health guidelines.¹⁴⁵

Randomization will be 1:1:1:1, stratified by gender, and by study site. To ensure balance with respect to the number of participants in each arm, we will use the permuted blocks strategy (using random block sizes of 4 and 8 because the study is not double-blinded).¹⁴⁶ To allow for simultaneous enrollment at multiple sites, we will use pre-printed scratch cards revealing randomization arm as in our previous studies.

This will be an open label study as we will not be able to blind participants or research assistants to the study arm. However, we will not reveal study arm to clinic counselors and clinicians so all study arms will receive the same standard clinical and counseling procedures.

[figure not shown]

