Study participants will be given information on the TB preventive therapy (INH) as well as Vitamin B-6. Participants will also be given instructions on how to use the MEMS device. The study staff will be trained to assess for all possible side effects of INH and Vitamin B-6 and will follow established protocols for identifying and monitoring any ongoing adverse events, including referrals to treatment. Study participants will be actively monitored for adverse events, particularly those related to INH, and Vitamin B-6 as in the most recent FDA's Drug Safety Announcement. Symptoms will be assessed at each follow-up study visit for the duration of treatment (at 2 weeks, 1, 2, 3, 4, 5, and 6 months), and additionally at 7 months, as needed for those who develop hepatotoxicity. RAs will document hepatotoxicities and side effects on CRFs, completed in real-time, as they receive the information from the participants, and submit completed forms to the study physicians for weekly review.

Other risks

- **Tuberculin Skin Testing (TST):** Risks of TST testing with subcutaneous placement of purified protein derivative (PPD) are rare, but include a very low risk of a severe allergic reaction to the skin test (<https://www.cdc.gov/tb/publications/factsheets/testing/skintesting.htm>). Participants with a history of a severe reaction to a TST in the past will not be given a TST during this study.
- The loss of confidentiality may lead to disclosure of HIV infection, TB infection, or disclosure of drinking status. Stigma associated with such disclosure may include social harms such as disruption of family (e.g., breakup of couples following HIV detection in one spouse), discrimination (e.g., a loss of employment or status in community), physical harm such as domestic violence (e.g., acts of physical violence directed at people who have been diagnosed with HIV), and psychological harm such as embarrassment (e.g., being questioned by family members about alcohol use). There may be some discomfort with the nature of the interviews, since alcohol use will be discussed. There is also the very slight but present chance of a breach of confidentiality inherent in any study that handles confidential data.

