6.2. Protection against risks

All adverse events (AEs): The Field Coordinator will complete descriptions of AEs on an AE reporting form that will be sent promptly to the Principal Investigator (PI) and all study investigators. Additionally, AEs will be reported to the Data and Safety Monitoring Board (see below), which will conduct further review of data from the DIPT Study and re-evaluate the risks to the participants.

Planned procedure for protection from risks due to medications: Study participants will be given information on the medication and advice on how to take the prescribed medications. They will be advised on the dosage and told not to double up on pills if any are missed. The staff will be trained to assess for all possible side effects of the medications and will follow established protocols for identifying and monitoring any AEs. Study participants will be actively monitored for AEs, particularly those related to INH and Vitamin B-6. Symptoms will be assessed at each follow-up study visit (at 2 weeks, and 1, 2, 3, 4, 5, and 6 months; 7 months as needed for those who develop hepatotoxicity.) by a trained clinical officer, and participants will be trained to recognize symptoms of hepatotoxicity. ALT/AST testing will also occur at these visits. Results of the ALT/AST testing will be given to the RAs by each cohort's research laboratory within 24 hours of testing. All participants will be given the phone number of the clinical officer to call in case symptoms develop between visits. In the case of suspected toxicity, the clinical officer will notify one of the two study physicians, who will determine whether a Grade 3/4 toxicity has occurred, and will recommend stopping treatment if INH is considered the

cause. The physicians will be blinded of the participant's study arm. If hepatotoxicity is discovered by ALT/AST results after the patient has left the clinic, the RA will contact the participant immediately via phone to inform them, and will make a follow-up home visit to retrieve the dispensed medications from the participant. In addition, the clinical officer will notify the study clinic for continued patient follow-up. Study participants will remain in the study following treatment discontinuation for follow-up monitoring, but will no longer be eligible to receive incentives for positive IsoScreen urine tests.

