Women of childbearing age will be asked about possible pregnancy at each follow-up study visit for the duration of INH treatment (at 2 weeks, 1, 2, 3, 4, 5, and 6 months), and additionally at months 7-9, for those who do not complete the regimen within the first 6 months. Women who report that they may have become pregnant will be offered a urine pregnancy test. Women who are confirmed to be pregnant will be discontinued from INH treatment. Study participants who become pregnant will remain in the study following treatment discontinuation for follow-up monitoring, but will no longer be eligible to receive incentives for positive IsoScreen urine tests.

Individuals who are prescribed Dolutegravir (DTG) will not be enrolled into the study until they have been on DTG for at least 3 months, to prevent starting DTG and INH at the same time.

Participants who are discontinued from INH treatment (due to toxicities or pregnancy) may still be eligible to receive incentives from EtG testing if they are in study arms 2 or 4.

Planned procedure for protection from risks due to phlebotomy: Trained RAs (trained clinical officers) or laboratory technicians will collect all specimens using standard sterile procedures. The phlebotomist will report any complications resulting from blood draws to the field study coordinator, who will make an immediate report to the Principal Investigator. The Principal Investigator will take responsibility for reporting such AEs to the relevant IRBs and NIH within ten days.

Planned procedure for protection from risks due to TST: The RAs (trained clinical officers) will conduct the TST in participants using standard sterile procedures. RAs will report any complications resulting from the TST to the field study coordinator, who will make an immediate report to the Principal Investigator. The Principal Investigator will take responsibility for reporting such AEs to the relevant IRBs and NIH within ten days.

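### Grading of hepatotoxicity is blinded, but ascertainment and referral are not shown to be, so the symptom-dependent part of this outcome is open to detection that differs by arm

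*Protocol*

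**What the plan says.** **The blinded step.** Protocol section 5.7.1 defines the outcome as stopping treatment because of Grade 3/4 hepatotoxicity and says: "Study clinicians, blinded to intervention arm, will determine treatment discontinuation". Sections 6.2 and 6.4 repeat that the physicians who grade the event and recommend stopping do not know the arm.

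**Who is not blinded.** Section 5.3 says: "This will be an open label study as we will not be able to blind participants or research assistants to the study arm". It adds: "we will not reveal study arm to clinic counselors and clinicians".

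**What happens before the physician is involved.**
- Section 5.6: a research assistant (RA) receives the urine and runs the EtG dipstick (Arms 2 and 4) and the IsoScreen (Arms 3 and 4).
- Section 6.1: "RAs will document hepatotoxicities and side effects on CRFs, completed in real-time". Physicians review these forms weekly.
- Section 6.2: "Results of the ALT/AST testing will be given to the RAs". No other recipient is named.
- Section 6.2: a trained clinical officer assesses symptoms at visits. "In the case of suspected toxicity, the clinical officer will notify one of the two study physicians".
- Section 6.2, on skin testing: "The RAs (trained clinical officers) will conduct the TST in participants using standard sterile procedures". The paragraph on blood draws describes the RAs in the same way.

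**Which events depend on symptoms.** In section 5.7.1, symptoms decide an event only in the 3 to 5 x ULN band. Above 5 x ULN the enzyme value is enough. The SAP, under Secondary outcomes, counts an enzyme value of at least 5 x ULN (Grade 3) or 10 x ULN (Grade 4). Alternatively, it counts symptoms that meet pre-specified criteria, with no enzyme threshold attached.

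**The concern.** A blinded grader protects the outcome only for cases that reach the grader. Physicians grade when suspected toxicity is notified, so an event that nobody elicits, records or refers may never be graded.

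Two features could make detection differ by arm:

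- **Staff knowledge.** Follow-up EtG is run only in Arms 2 and 4, so what the RA knows about recent drinking differs by arm by design. That could prompt more or less probing for liver symptoms.
- **Participant motive.** Participants know their arm. Under section 6.2, someone taken off INH can no longer earn IsoScreen incentives but may still earn EtG incentives. Participants in Arms 3 and 4 therefore have a reason to under-report symptoms that those in Arms 1 and 2 lack.

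Less hepatotoxicity is part of the Aim 1 hypothesis (section 2.1), and section 3 gives lower hepatotoxicity risk as the reason for Aim 1. The SAP compares each of Arms 2, 3 and 4 with Arm 1 on this outcome. A difference could partly reflect who was asked and referred.

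**Working it through.** **Step 1. Trace each step and its blinding.**

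| Step | Done by | Blinded to arm? |
|---|---|---|
| Reporting symptoms | Participant | No (5.3) |
| Documenting side effects | RA (6.1) | No (5.3) |
| Assessing symptoms at visits | Clinical officer (6.2, 6.4) | Not stated |
| ALT/AST sampling | Fixed visits, all arms (5.5, Table 2) | Same schedule in every arm |
| Receiving ALT/AST results | RA (6.2) | No (5.3) |
| Notifying the physician | Clinical officer (6.2, 6.4) | Not stated |
| Grading and recommending a stop | Study physician (5.7.1, 6.2, 6.4) | Yes |

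The two unstated entries turn on one ambiguity. Section 5.3 withholds the arm from clinicians, which could cover clinical officers. Section 6.2 twice describes the unblinded RAs as trained clinical officers, which suggests that they are the same staff.

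A further gap is the late result. If an enzyme result shows hepatotoxicity after the participant has left, section 6.2 has the RA telephone and retrieve the medication. That sentence names no physician decision.

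**Step 2. Expected number of events.** The documents give no power calculation for this outcome, so there is no planned figure to reproduce. Section 3 gives a Grade 3/4 rate of 0.1 to 4.0%. With 680 participants randomized 1:1:1:1, each arm has 680 / 4 = 170.

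- Per arm: 170 x 0.001 = 0.17 to 170 x 0.04 = 6.8 events.
- Whole trial: 680 x 0.001 = 0.68 to 680 x 0.04 = 27.2 events.

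**Step 3. Illustrate the bias.** Let p be the true rate in both arms, s the share of events that depend on symptoms, and d the share of those that are detected. Enzyme-only events are taken as fully detected.

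Observed rate = p x [(1 - s) + s x d]

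Take p = 4% (top of the protocol's range), with d = 0.90 in one arm and 0.70 in the other. The values of s and d are assumptions; the documents give none.

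| s | Observed at d = 0.90 | Observed at d = 0.70 | Relative difference | Events per 170 |
|---|---|---|---|---|
| 0 | 4.0% | 4.0% | 0% | 6.80 v 6.80 |
| 0.5 | 0.04 x 0.95 = 3.8% | 0.04 x 0.85 = 3.4% | 1 - 3.4/3.8 = 10.5% | 6.46 v 5.78 |
| 1 | 0.04 x 0.90 = 3.6% | 0.04 x 0.70 = 2.8% | 1 - 2.8/3.6 = 22% | 6.12 v 4.76 |

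**Step 4. Effect on the test.** Take a harsher case: half of events depend on symptoms, all of them are found in one arm and half of them are missed in the other. Rates are 4% v 0.04 x (1 - 0.5 x 0.5) = 3%, or 170 x 0.01 = 1.7 events. A normal approximation puts the chance of a significant result in that direction at about 7%, against a nominal 2.5%. The approximation is rough with so few events.

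**The case against.** A reader might infer that the safety outcome as a whole is unblinded. The documents do not support that. Grading and the stopping decision define the outcome, and both belong to blinded physicians. The sentence in section 5.7.1 claims no more than that.

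A reader might also take it as stated that unblinded RAs elicit the symptoms and raise the suspicion. Sections 6.2 and 6.4 give those tasks to a clinical officer, and section 6.2 elsewhere uses the two titles separately. That they are the same people is a fair inference from two parenthetical remarks, but it is not stated. Likewise, naming the RAs as recipients of enzyme results does not exclude the physicians.

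There are real safeguards. Enzymes are tested on one schedule in all arms, laboratory data undergo weekly checks (section 5.8), physicians review the forms weekly, and a monitoring board with an added hepatologist reviews safety data (section 6.4). In the protocol no event can rest on symptoms alone. The 22% figure requires every event to depend on symptoms, which does not fit scheduled enzyme testing.

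These points limit the concern to the symptom-dependent events. They do not remove it. Reviewing forms cannot recover symptoms that were never elicited. Nothing states that the clinical officer is blinded. The SAP's symptom route is also wider than the protocol's.

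**Conclusion.** The concern holds for ascertainment and referral, and it does not extend to adjudication. What is open to differential detection is the symptom-dependent part of the outcome: the 3 to 5 x ULN band in the protocol and the symptom route in the SAP. Events found only by scheduled enzymes are largely immune.

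Neither the size nor the direction can be derived from the documents. With a 4% true rate, half of events symptom-dependent and 90% v 70% detection, the observed rates are 3.8% and 3.4%. That is about 11% lower with no true effect, or 6.46 - 5.78 = 0.68 of an event per arm. It is zero if no events depend on symptoms. With at most about 6.8 events expected per arm, one or two events found or missed would visibly move the estimate. A false significant result is less likely.

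This is a secondary outcome, and neither primary outcome is affected. The point still merits a change, because the outcome carries the trial's safety argument and the remedy uses data already scheduled for collection.

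**What to change.** **Main change, in the SAP.** Add a supportive laboratory-only outcome: any scheduled ALT or AST beyond the 5 x ULN limit already in the documents, in all arms, regardless of referral or discontinuation. Analyse it with the same comparisons as the planned outcome (Arms 2, 3 and 4 each against Arm 1). Counting only scheduled tests keeps out the extra tests that follow a referral. Report the number of scheduled tests done per arm as well, because incentives may affect attendance.

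The cost is a sentence or two in the SAP and no new tests. The downside is that this is a different endpoint from discontinuation and omits symptom-defined events. It should therefore stand beside the planned outcome and not replace it.

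**Wording.** State which steps are blinded, whether the clinical officer is an RA, who receives ALT/AST results, and who decides when a late result leads the RA to retrieve medication. Reconcile the hepatotoxicity definitions in Protocol section 5.7.1 and the SAP's Secondary outcomes. They differ on the role of symptoms and on whether 5 x ULN itself counts. No view is taken here on which is right.

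**Any remaining visits.** Copy every ALT/AST result to the blinded physician, and complete the symptom form before the urine test is read. Neither needs extra staff. The SAP is dated August 2022 and recruitment began in April 2018, so these steps may come too late for many visits. The laboratory-only analysis does not depend on them.

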5.7.2. Other measures

Covariates: Several covariates (Table 3) will be used to describe the study population (demographics, mental and physical health variables, alcohol use and HIV viral suppression at baseline) that may act as potential confounders if not equally randomized.

Moderators: We will examine gender as a potential moderator of intervention effects because drinking patterns between men and women differ widely in SSA,^{162,163} and there is some evidence that alcohol interventions may not be equally effective among men versus women.¹⁶⁴⁻¹⁶⁷ We will also examine alcohol use severity at baseline (AUDIT score >16) as a moderator because dependent drinkers may have differing responses to alcohol interventions.^{168,169} To examine whether baseline measures of sensitivity to economic incentives and psychological measures of treatment readiness impact intervention efficacy, we will examine level of delay discounting (measured using scales of time preferences we have used in Kenya¹⁷⁰) and a treatment readiness scale.¹⁷¹

Table 3. Covariates			
Domain	Baseline	3-, 6- and 12-month	Individual variables
Demographics	◆		Age, sex, religion, household assets (as a measure of SES), ¹⁷² and literacy
Health	◆		Medical Outcomes Study-HIV scale for quality of life and overall physical and mental health functioning, ¹⁷³⁻¹⁷⁷ body mass index, CD4 cell count, active hepatitis B viral infection, smoking, and duration on ART
Alcohol use	◆	◆	AUDIT, AUDIT-C, drinking patterns (days of the week), bar attendance, heavy drinking measured by level of intoxication
ART adherence	◆	◆	ART adherence Single Item Rating Scale, ^{178,179} Visual analog scale, viral suppression (the direct result of adequate adherence)
Psychosocial scales	◆		Center for Epidemiologic Studies Depression Scale (16 items), ¹⁸⁰ Stages of Change Treatment Eagerness Scale (19 items) ¹⁷¹
Discount rate (high vs. low)	◆		Time preferences (a measure of present bias and temporal discounting; i.e. tendencies towards instant versus delayed gratification), highly predictive of HIV mortality ¹⁷⁰

5.8. Data management

Data management and quality assurance will be conducted separately for the DIPT 1/2 and DIPT 2/2 cohorts, leveraging the data management systems already in place within each site. As in the Uganda URBAN ARCH and SEARCH cohorts, tracking information will be entered into a database that will generate reminders for follow-up visits. The questionnaire data, assessments of side effects at refill visits, and laboratory results will be entered into a laptop computer in Uganda while offline, and later uploaded to a secure server at UCSF. The MEMS adherence data will be uploaded to UCSF monthly, or more frequently as needed. All study assessments will be identical at both sites for data harmonization. At each site, all data will undergo weekly checks for completeness and range criteria. We will pool the data from the two sites for analysis.

5.9. Statistical analysis plan

This study will use an intent-to-treat analysis including all participants according to their randomized assignment (excluding pilot participants). Descriptive statistics will be calculated for all variables at baseline to characterize the study population and assess whether there appear to be differences across randomized groups; any baseline covariate that differs by study arm despite randomization will be included in adjusted analyses.

Up to two patients at each site will be recruited as pilot participants prior to the official start of the trial. Enrollment of pilot participants will enable staff to trouble-shoot any unanticipated issues in the SOPs during implementation. Data from these individuals will not be included in the analyses outlined below.

